Slope of probing depth, time 1 to 3	57	-1.47	0.015	-0.10632	0.323886
Slope of gingivitis index, time 1 to 3	57	-0.99	-0.03	-0.24351	0.221807
Slope of plaque score, time 1 to 3	57	-1.53	-0.045	-0.45254	0.358255
Valid N (listwise)	57				

Global Probing Depths (GPD)

Global probing depth (GPD) collected at the first visit did not differ significantly between groups; control group's (Group A) initial GPD was 2.76 (SEM = 0.092) interval, and 2.68 (0.071) for test group (Group X), a non-significant statistical difference ($p = 0.48$).

Neither did the GPD score differ between final visits of control group (Group A) (GPD = 2.64 (0.130) and test group (Group X) (GPDI = 2.37, (0.166), $t = 1.27$, $df = 55$, $p = 0.28$. Nonetheless, the GPD decreased significantly for control group (Group A), ($p = 0.028$; for X, $p < 0.001$) for both groups, but the group decreases were not significantly different from each other. Both mouthwashes reduced probing depth similarly.

The key signal of treatment effectiveness is a statistically significant treatment-by-time interaction, where improvement over time is greater for one treatment than another. Nearly parallel lines in Figure 2 and statistical testing indicated no appreciable and significant treatment-by-time interaction for GPD (See Figure 2, Figure 3).

Figure 2. Interaction plot showing that group assignment did not interact with time for probing depth.

[figure not shown]

Figure 3. Boxplots of probing depth results from treatment by control group (Group A) and test group (Group X). Probing depth was not affected differentially by the mouthwash treatments. Both conditions reduced probing depth slightly but not statistically significant.

Global Plaque Score

Control group (Group A) and test group (Group X) differed significantly in global plaque score (GPS) at initial assessment, requiring an additional analysis of covariance to confirm that a significant time by treatment interaction was not an artifact from the initial difference in GPS (See interaction plot, Figure 4, detailed in Figure 5). The test group's (Group X) initial average GPS was 3.00 (SEM = 0.071) versus 2.35 (0.097) for the control group (Group A), a significant difference ($t = -5.45$, $df = 50$, $p < 0.001$). At assessment 3, the last observation, the test group's (Group X) GPS (1.57, SEM = 0.110) was significantly lower than that for the control group (Group A); GPS = 1.98 (0.110), $t = 2.633$, $df = 55$, $p = 0.011$.

[figure not shown]

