The gingivitis index is based on the Gingival Index system,² in this case, the global gingival index is GGI. The GGI was also significantly higher for the test group (Group X) at the initial visit; for the test group (Group X) = 2.03 (0.025) and GGI for the control group (Group A) = 1.91 (0.035), ($t = -2.89$, $df = 55$, $p = 0.006$). Figure 6 illustrates a potential interaction between treatment and time of observation that required statistical consideration and control. Again, GGI for visit 1 was used as a covariate so as not to over-estimate treatment effects on GGI represented in a time-by-treatment interaction. The ANCOVA upheld a statistically significant ($t = 2.12$, $df = 51$, $p = 0.039$) between treatments. Boxplots of the GGI across visits is shown in Figure 7. The test group (Group X) reduction in GGI was 27.3% versus the control group's (Group A) reduction of 20.4%, also statistically significant difference by repeated measures analysis of variance ($F = 8.141$, $df = 1$, $p = 0.0046$).

[figure not shown]

Figure 6. Interaction plot showing group assignment interacting with time on gingival index measures (GGI).

[figure not shown]

Figure 7. Boxplots of gingival index measures comparing treatment control group (Group A) and test group (Group X). Test group (Group X) started with higher gingival index levels. Gingival index decreased more and faster in test group (Group X) than in the control group (Group A), though both decreased significantly.

Differential Effects of Mouthwashes on Implants in Control Group (Group A) and Test Group (Group X)

Of particular interest was the specific effect that control mouthwash (rinse A) and test mouthwash (rinse X) might have on implant and non-implant sites across the three outcomes. Table 4 illustrates the overall study results of treatments and implants on the three outcomes. Probing depth was not different between treatments for implant and non-implant sites. Plaque and gingival indexes were improved significantly under test rinse Treatment (rinse X), with details described in Tables 5, 6, and 7 below. In addition, implant sites improved at a faster rate under test rinse Treatment (rinse X) conditions for both gingivitis and plaque.

Table 4. Omnibus test for main effects and interactions of control mouthwash (rinse A) and test mouthwash (rinse X) on implant and non-implant sites.

Sites of Implants responding differently to treatment					
All outcomes: measures in table					

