Figure 8. No differential effects of mouthwashes on probing depth between implant and non-implant sites. Both groups showed only slight decreases in probing depth. Note that in control condition (rinse A), probing depth was higher for the implant group at baseline.

Implants and Gingival Index

Implant versus normal oral sites also showed a significant main effect ($F = 79.0$, $df = 1$, $p < 0.001$) indicating more and faster gingival index improvement in test group (Group X) for both implant and non-implant sites. Test group (Group X) implants decreased in gingival index scores by 83% while implants in control group (Group A) decreased by 57%. The non-implant sites for control group (Group A) decreased by 23% and for test group (Group X) by 50%. The rate of change was faster for test group (Group X) implants than for control group (Group A) and faster than test group (Group X) non-implant sites. Test Treatment (rinse X) members' implants decrease in gingival index measured 26% versus 19% for those in control group (Group A).

[figure not shown]
Table 6 indicates a strong and statistically significant difference between implant and non-implant sites between and within groups – over time. Figure 9 illustrates the higher gingivitis index in test group (Group X) and greater and faster decrease of gingivitis in test group (Group X).

Table 6. Summary results of general linear model of gingival index measures.

Tests of Between-Subjects Effects

Gingivitis					
Source	Type III Sum of Squares	df	Mean Square	F	Sig.
Intercept	1207.001	1	1207.001	11073.258	0.000
implant	9.949	1	9.949	91.274	0.000
group	9.177	1	9.177	84.187	0.000
implant * group	8.613	1	8.613	79.021	0.000
Error	11.118	102	0.109		

Figure 9. Significant differential effects of mouthwashes on gingival index at implant sites. Both groups showed significant decreases in plaque, but the test group (Group X) reduced gingival index scores more and at a faster rate. Note the difference in gingival index scores at the beginning of the trial.

Implants and Plaque

Plaque scores (PS) for both implant and non-implant plaque scores were higher in the test group (Group X) (2.99 (0.071)) than in the control group (Group A) (2.35 (0.100)) at the first visit, $t = 5.45$, $df = 55$, $p < 0.001$. As with gingival index, PS decreased more for test group (Group X) patients (-0.799 (0.109)) than for control group (Group A) (-0.156 (0.064)) in both implant and non-implant sites, $t = 5.75$, $df = 55$, $p < 0.001$.

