There is a clear advantage to using ClōSYS® Ultra Sensitive oral rinse treatment (test rinse X) in terms of plaque and gingival index. In addition, ClōSYS® Ultra Sensitive oral rinse (test rinse X) appeared to have a preferential benefit for implant sites, over both control treatment (placebo rinse A) and over non-implant sites. The ClōSYS® Ultra Sensitive rinse (test rinse X) significantly reduced the plaque index and gingival index as compared to initial measures and those in control group (placebo rinse A) ($p < 0.001$). The observation of higher initial gingivitis scores for the ClōSYS® Ultra Sensitive oral rinse (test rinse X) did not affect the superiority of this test group treatment. In controlling for the inequality at baseline, and analysis of covariance showed the reduction of the plaque score remained significantly better in the ClōSYS® Ultra Sensitive oral rinse group (test rinse X) than for the control group (placebo rinse A) ($p < 0.001$). Also, using pre-post difference scores and slopes of the scores over time showed the treatment effect to be robust to the mismatch of initial levels of gingivitis and plaque ($P < 0.001$ for both).

Both groups improved from the use of mouthwashes, but the ClōSYS® Ultra Sensitive oral rinse (test rinse X) improved more and at a faster rate ($p < 0.001$) compared to the control group (placebo rinse A). There was no apparent effect on periodontitis between the two intervals in which it was measured.

Implant sites were significantly more ($p < 0.001$) and faster ($p < 0.001$) improved in the ClōSYS® Ultra Sensitive oral rinse group (test rinse X) than the other non-implanted teeth and in the control group (placebo rinse A).

Both ClōSYS® Ultra Sensitive oral rinse (test rinse X) and placebo rinse (rinse A) tested are safe to oral tissues and did not show any adverse effects.

Both ClōSYS® Ultra Sensitive oral rinse (test rinse X) and placebo rinse (rinse A) tested are safe to oral tissues and do not have any adverse effects.

Signature Page

[name]

Principal Investigator

[name] [name], PhD

REFERENCES

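### At implants the test arm ends Day 90 with higher MGI than placebo (about 1.99 v 1.49); superiority there rests on unadjusted change, and its sign after baseline adjustment cannot be determined

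*Combined protocol and SAP*

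**What the plan says.** All references are to the combined protocol and SAP.

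- **[11] Statistical Evaluation** names MGI as the measure for the primary objective, without restricting it to implants.
- **Global Plaque Score** introduces ANCOVA because the arms differed significantly at the first visit, "requiring an additional analysis of covariance to confirm that a significant time by treatment interaction was not an artifact". **Global Gingival Index Score** does the same for whole-mouth MGI: "GGI for visit 1 was used as a covariate so as not to over-estimate treatment effects on GGI" (t = 2.12, df 51, p = 0.039). No baseline-adjusted result is reported for implants. Tables 4 to 7 show no baseline covariate.
- **Table 1** gives baseline implant MGI as 2.82 (SEM 0.049) in 26 test patients and 2.06 (SEM 0.048) in 27 placebo patients.
- **Implants and Gingival Index** gives two sets of falls. The first says that test-arm "implants decreased in gingival index scores by 83% while implants in control group (Group A) decreased by 57" per cent, and that placebo non-implant sites "decreased by 23% and for test group (Group X) by 50" per cent. The second says that test-arm "implants decrease in gingival index measured 26% versus 19% for those in control group (Group A"). The same section cites F = 79.0 as "indicating more and faster gingival index improvement in test group (Group X) for both implant and non-implant sites".
- **Conclusions** say that the higher initial gingivitis scores "did not affect the superiority of this test group treatment". For gingivitis they rely on the statement that "using pre-post difference scores and slopes of the scores over time showed the treatment effect to be robust to the mismatch". Two further sentences claim that implants benefited preferentially, over placebo and over natural teeth.

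**The concern.** Implants are the sites that define peri-implant mucositis, and MGI is the primary measure. At implants the arms start 0.76 MGI points apart. Whole-mouth MGI differed by only 0.12 (2.03 v 1.91), yet that gap was judged to need a covariate.

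Difference scores and slopes do not adjust for baseline. When one arm starts much higher, its larger fall may partly be regression to the mean, so these analyses cannot show that the result is robust to the gap. A reader also cannot see where each arm finished at the implants, because only baseline values are tabulated. At stake is whether the implant claims in the Conclusions have support on the primary measure.

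**Working it through.** **1. What the printed falls mean.** Table 5 is captioned as probing depth but is labelled GGI inside. Its error df of 102 fits 27 + 26 patients at two site types (106 units less 4 cells). For the Day 0 to Day 90 contrast (change divided by √2), let v = 2/27 + 2/26 = 0.1510. Then SS(time) = (mean change)²/2 × 16/v, and each interaction SS = (contrast)²/2 ÷ (v/4).

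Take the falls as points: test implants 0.83, placebo implants 0.57, test teeth 0.50, placebo teeth 0.23.

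| Term | Contrast (points) | SS, read as points | SS, read as percentages | Table 5 |
|---|---|---|---|---|
| Time | 0.5325 | 15.02 | 81.1 | 15.113 |
| Time × implant | 0.335 | 1.486 | 14.3 | 1.507 |
| Time × group | 0.265 | 0.930 | 10.0 | 0.941 |
| Time × implant × group | -0.005 | 0.0003 | 1.16 | 0.001 |

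Only points reproduce the table. The literal percentages also conflict with the test arm's whole-mouth fall of 27.3%, which cannot be smaller than falls of 50% at teeth and 83% at implants.

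**2. Day 90 implant MGI.**
- Points: test 2.82 - 0.83 = 1.99; placebo 2.06 - 0.57 = 1.49; gap +0.50, test higher.
- The 26%/19% pair: 2.82 × 0.74 = 2.09; 2.06 × 0.81 = 1.67; gap +0.42, test higher.
- Literal 83%/57%: 2.82 × 0.17 = 0.48; 2.06 × 0.43 = 0.89. This would reverse the direction, but step 1 rules it out.

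**3. Check without the percentages.** Table 6, solved for three-visit cell means with signs as in Table 1, gives implant means of 2.46 (test) and 1.79 (placebo). Assuming one or two visits instead would put the overall mean at 3.38 or 2.39, above the baseline mean of (2.06 + 1.87 + 2.82 + 2.01)/4 = 2.19. If scores never rose between visits:
- Test Day 90 is at least 3 × 2.46 - 2.82 - 2.82 = 1.74.
- Placebo Day 90 is at most (3 × 1.79 - 2.06)/2 = 1.66.

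Test is again higher.

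**4. Baseline gap.** 2.82 - 2.06 = 0.76; SE = √(0.048² + 0.049²) = 0.069; about 11 SEs.

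**5. Unadjusted change.** 0.83 - 0.57 = 0.26 in favour of test. If the pooled Table 5 error applies to implants, the change SD is √(2 × 2.737/102) = 0.232, the SE is 0.232 × √(1/27 + 1/26) = 0.064, and t is about 4.1.

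**6. Adjusted difference (test minus placebo; negative favours test).** It equals the Day 90 gap - b × 0.76, where b is the within-arm slope of Day 90 on baseline. b is not reported.

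| b | 0.50 - 0.76b | 0.42 - 0.76b (26%/19% pair) |
|---|---|---|
| 0 | +0.50 | +0.42 |
| 0.5 | +0.12 | +0.04 |
| 0.55 | +0.08 | 0 |
| 0.66 | 0 | -0.08 |
| 0.75 | -0.07 | -0.15 |
| 1 (plain change) | -0.26 | -0.34 |

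To show plausible values of b, take the baseline SD as 0.25 (0.048√27 and 0.049√26), the change SD as 0.232, and assume a Day 90 SD. Then b = (baseline variance + Day 90 variance - change variance)/(2 × baseline variance). An assumed Day 90 SD of 0.20, 0.25 or 0.30 gives b = 0.39, 0.57 or 0.79, and an adjusted difference (0.50 gap) of +0.20, +0.07 or -0.10.

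**7. The cited tests.** F = 79.0 is the implant × group term of Table 6 (79.021), a between-subjects test of level averaged over visits. It reflects higher test-arm implant scores, not a faster fall. The term for an extra MGI effect at implants is time × implant × group in Table 5, with p = 0.840. The between-arm difference in fall is 0.83 - 0.57 = 0.26 at implants and 0.50 - 0.23 = 0.27 at teeth. Implants did fall more than teeth, but in both arms.

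**The case against.** The quoted sentence concerns gingivitis in general, and for the whole mouth it has reported support. ANCOVA on whole-mouth MGI gives p = 0.039, and the printed means and falls put test slightly lower at Day 90: 2.03 × (1 - 0.273) = 1.48 v 1.91 × (1 - 0.204) = 1.52. Unadjusted change at implants also favours test. Both points stand.

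Four stronger readings are tempting, and the documents do not support them.

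- **That the test rinse did worse than placebo at implants.** The raw Day 90 gap may simply carry forward part of the 0.76 baseline gap. The adjusted sign is unknown in either direction.
- **That no effect remains on a log scale**, because the relative falls are 0.83/2.82 = 29.4% and 0.57/2.06 = 27.7%. Data Management and Statistical Analysis says that a gamma log link was used in most tests, but not which ones. Tables 5 and 6 are general linear models, and Table 5 reproduces on the raw scale. The 26%/19% pair would give a ratio of 0.74/0.81 = 0.914, about 9% in favour of test.
- **That Day 90 implant MGI was withheld.** It is absent from the text and tables, but Figure 9 is not shown in this copy and may plot it.
- **That no adjusted implant analysis was ever run.** The documents show only that none is reported.

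**Conclusion.** The concern holds for the implant sites. Day 90 implant MGI was about 1.99 (test) v 1.49 (placebo), or 2.09 v 1.67 on the other printed pair. Superiority on implant MGI rests on unadjusted change of 0.26 points across a 0.76-point baseline gap. After adjustment the sign turns at b of about 0.55 to 0.66, and the documents do not fix b. The claim of a preferential MGI benefit at implants over teeth is not supported by Table 5.

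The Day 90 values rest on Table 1 and on reading the first set of falls as points, which Table 5 confirms. Their direction is supported by Table 6 if scores did not rise between visits. The verdict does not extend to whole-mouth MGI or to plaque.

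**What to change.** - In [11], replace ANCOVA prompted by a significant baseline difference with one rule: Day 90 score on arm plus the baseline of the same score, run separately for implants and for natural teeth.
- Print Day 90 implant MGI by arm with 95% CIs, and show how far the two baseline distributions overlap, since the adjusted estimate depends on that overlap.
- In Implants and Gingival Index, correct the percentages that are points, reconcile the two sets of falls, and stop citing F = 79.0 as evidence of faster improvement. Correct the Table 5 caption and the probing-depth text that relies on it.
- In the Conclusions, limit the quoted sentence to whole-mouth MGI, citing the ANCOVA p = 0.039. Withdraw or qualify the two implant sentences for MGI unless the adjusted implant analysis supports them.

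The cost is one rerun on data already held, plus rewording. The downside is that the implant claim becomes weaker or is withdrawn.

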From raw data of individual teeth, each patient received a global index of periodontal disease, gingival index, and plaque for each visit. The global index for each of these measurements was found by dividing the sums of patient probing depth, gingival index, and plaque findings collected for each tooth by the number of teeth assessed. Over the three assessment periods, global scores of probing depth, gingival index, and plaque were collected for the first and last visits with probing depth scores not collected during the second visit. These outcomes are measured as individual slopes of responses across the three observation visits. The slope represents the rate of change.

The overall view of the response of each measure to the treatment group is summarized in the following general linear model Table 2. Table 3 shows the cell statistics for the slopes of each condition and outcomes reported in Table 2.

Table 2. Master table of variance components attributable to treatment on individual rates of change on the three measures: probing depth, gingival index, and plaque.

Source	Variable	Type III SS	df	MS	F	Sig.
Group	Slope of probing depth, time 1 to 3	0.125	1	0.125	1.191	0.28
	Slope of gingivitis index, time 1 to 3	0.485	1	0.485	11.748	0.001
	Slope of plaque score, time 1 to 3	4.019	1	4.019	69.751	0.000
Error	Slope of probing depth, time 1 to 3	5.75	55	0.105		
	Slope of gingivitis index, time 1 to 3	2.27	55	0.041		
	Slope of plaque score, time 1 to 3	3.169	55	0.058		
Total	Slope of probing depth, time 1 to 3	6.519	57			

Slope of gingivitis index, time 1 to 3	6.135	57
Slope of plaque score, time 1 to 3	18.861	57
Corrected Total	Slope of probing depth, time 1 to 3	5.875
	Slope of gingivitis index, time 1 to 3	2.755
	Slope of plaque score, time 1 to 3	7.187
	R Squared = .021 (Adjusted R Squared = .003)	
	R Squared = .176 (Adjusted R Squared = .161)	
	R Squared = .559 (Adjusted R Squared = .551)	

Table 3. Details of cell statistics for analysis described in Table 2.

Descriptive Statistics					
	N	Minimum	Maximum	Mean	Std. Deviation
Probing depth at time 1	57	2.04	4.63	2.71614	0.432843
Probing depth at time 3	57	0	4.42	2.50351	0.804056
Gingivitis index at time 1	57	1.41	2.23	1.97158	0.172065
Gingivitis index at time 2	57	0	2	1.71754	0.364095
Gingivitis index at time 3	57	0	1.92	1.48456	0.451688
Plaque score at time 1	57	1.47	3.54	2.67895	0.555475
Plaque score at time 2	57	0	3.11	2.19614	0.596444
Plaque score at time 3	57	0	2.92	1.77386	0.618124

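### The Conclusions use change scores and slopes to say the gingivitis effect withstands the baseline imbalance at P < 0.001; neither adjusts for baseline, and the only reported baseline-adjusted MGI result (p = 0.039) is left out of them

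*Combined protocol and SAP*

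**What the plan says.** Section [11], Statistical Evaluation, lists MGI under the primary objective and makes the treatment-by-time interaction the primary hypothesis, with rate of change as a question separate from total change.

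The arms differed at baseline. Global MGI was 2.03 in the test arm and 1.91 in the control arm (p = 0.006). At implants it was 2.82 against 2.06 (Table 1).

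The Conclusions say that difference scores and slopes "showed the treatment effect to be robust to the mismatch of initial levels of gingivitis and plaque", adding P < 0.001 for both. They also say that the test rinse "improved more and at a faster rate ($p < 0.001$) compared to the control group (placebo rinse A").

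The reported tests on global MGI are:
- Table 2, Group row, with 55 error df: "Slope of gingivitis index, time 1 to 3 0.485 1 0.485 11.748 0.001".
- Global Gingival Index Score, with the first visit as covariate: "The ANCOVA upheld a statistically significant ($t = 2.12$, $df = 51$, $p = 0.039$) between treatments". The section explains that the covariate was used to avoid over-estimating the treatment effect.
- Same section: "repeated measures analysis of variance ($F = 8.141$, $df = 1$, $p = 0.0046").

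Table 3 gives the slope as "Slope of gingivitis index, time 1 to 3 57 -0.99 -0.03 -0.24351 0.221807" and the last visit as "Gingivitis index at time 3 57 0 1.92 1.48456 0.451688". The columns are N, minimum, maximum, mean and SD.

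**The concern.** A reader takes the robustness sentence to mean that the baseline imbalance was dealt with for both outcomes and that the MGI result stayed below 0.001. A change score subtracts baseline with a fixed coefficient of 1. It does not estimate how follow-up depends on baseline, so it cannot test whether the imbalance explains part of the difference. The slope model in Table 2 has only Group and Error terms.

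The report used ANCOVA for this purpose on both outcomes, but its Conclusions carry forward only the plaque result. At stake is the stated strength of evidence on MGI, and whether the claim of faster improvement has any support of its own in the global scores.

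**Working it through.** **1. Reported p values.** Table 2: F = 0.485 / (2.27/55) = 11.75, against 11.748 printed. F(1,55) = 11.748 gives p = 0.00116, which rounds to the printed 0.001. To fall below 0.001, F would have to exceed 12.09. For the ANCOVA, t = 2.12 on 51 df gives p = 0.039, as printed.

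**2. Slope and change are one test.** Half the difference between the Table 3 means, (time 3 - time 1)/2, against the printed mean slope:

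| Measure | Half the change | Printed slope |
|---|---|---|
| Probing depth | (2.50351 - 2.71614)/2 = -0.10632 | -0.10632 |
| MGI | (1.48456 - 1.97158)/2 = -0.24351 | -0.24351 |
| Plaque | (1.77386 - 2.67895)/2 = -0.45255 | -0.45254 |

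For plaque, the reported change-score t of 8.35 is the square root of the slope F: sqrt(69.751) = 8.35.

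**3. Day 14 has no weight.** A least-squares slope on Days 0, 14 and 90 would use weights of -0.0074, -0.0044 and +0.0118 per day. The reported slope treats the visits as equally spaced, which gives Day 14 a weight of zero. Yet (1.97158 - 1.71754)/(1.97158 - 1.48456) = 52% of the fall in mean MGI had occurred by Day 14. That is 0.018 per day up to Day 14 and (1.71754 - 1.48456)/76 = 0.003 per day afterwards. The reported slope carries no information on rate beyond the total change.

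**4. What adjustment does.** I rebuilt a Gaussian ANCOVA of change on baseline from the Table 3 SDs, the Table 2 sums of squares and the baseline arm means, with N = 57 and arms of 27 and 30 assumed.
- k = 27 x 30/57 = 14.21. Unadjusted difference in MGI change: -2 x sqrt(0.485/14.21) = -0.369.
- Total sums of squares: baseline 56 x 0.172065² = 1.658; change 4 x 56 x 0.221807² = 11.020; time 3 56 x 0.451688² = 11.425. Total cross-product: (11.425 - 1.658 - 11.020)/2 = -0.627.
- Within arms, baseline difference 0.12: cross-product -0.627 + 14.21 x 0.12 x 0.369 = about 0.003; baseline 1.658 - 14.21 x 0.12² = 1.453. Coefficient of change on baseline: about 0.002.
- Adjusted difference -0.37. SE = sqrt[(4 x 2.27/54) x (1/27 + 1/30 + 0.12²/1.453)] = 0.116. 95% CI -0.60 to -0.14, F = 10.13, p = 0.0024.
- The same steps for plaque (baseline 3.00 against 2.35) move the difference from -1.06 to -0.92 and F from 69.75 to about 35. The reported plaque ANCOVA has F = 34.82, which supports the method.

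Arm splits from 26/31 to 30/27 leave these MGI results unchanged to two decimals. For plaque, adjustment halves F, so a change-score test is no substitute for it.

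**5. Is there a source for P < 0.001 on MGI?** Table 5 has Time*group F = 35.047 on 1 and 102 df. It is headed GGI but captioned probing depth. Implants and Gingival Index gives falls of 83%, 57%, 23% and 50%. Read as point falls (0.83 and 0.57 at implants, 0.23 and 0.50 elsewhere), they match Table 5, assuming 106 = 2 x 53 records and a (time 3 - time 1)/sqrt(2) contrast:
- Mean fall: (0.83 + 0.57 + 0.23 + 0.50)/4 = 0.533; Table 5 gives sqrt(2 x 15.113/106) = 0.534.
- Arm difference: 0.665 - 0.400 = 0.265; Table 5 gives 2 x sqrt(2 x 0.941/106) = 0.266.
- Implant difference: 0.700 - 0.365 = 0.335; Table 5 gives 2 x sqrt(2 x 1.507/106) = 0.337.
- Three-way contrast: 0.33 - 0.34 = -0.01; Table 5 gives F = 0.041.

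Table 5 is therefore very probably MGI. Halving F for two records per patient gives 17.5 on 51 df, p = 0.0001. The table has no baseline term.

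**The case against.** The strongest reply is that the Conclusions sentence never says global. Table 5 is then a reported MGI change test below 0.001, so the p value has a source. That stands, and it rules out the reading that P < 0.001 was stated with nothing behind it. It does not rescue the sentence, because a test with no baseline term cannot show robustness to baseline.

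A second reply is that 0.00116 against 0.001 is a matter of rounding, and that the rebuilt ANCOVA leaves global MGI at -0.37, so the conclusion may be right even if the argument is not. Both parts are fair. The point is the invalid argument and the omitted 0.039, not the third decimal.

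A reader might also infer that the MGI results contradict one another. The documents do not establish that:
- "The test group (Group X) reduction in GGI was 27.3" per cent, against 20.4% in the control arm, need not mean falls in the global arm means. The point falls in step 5 over the Table 1 baselines give (0.83 + 0.50)/(2.82 + 2.01) = 27.5% and (0.57 + 0.23)/(2.06 + 1.87) = 20.4%.
- The repeated-measures p of 0.0046 is too small for 171 global scores (57 x 3), but the implant/non-implant long file has 53 x 2 x 3 = 318, and about 312 error df gives 0.0046.
- The ANCOVA df of 51 is not a safe guide to the number analysed. The baseline plaque t of 5.45 is printed once with 50 df and once with 55.
- Implant falls of 83% and 57% in one sentence and 26% and 19% in another may be points and percentages, which are different quantities. The base of the second pair is not stated.

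**Conclusion.** The point holds. Difference scores and slopes are one unadjusted test for the global scores and cannot show robustness to the baseline mismatch. For global MGI the reported p values are 0.00116, 0.0046 and, with baseline adjustment, 0.039. The Conclusions omit the last while citing its plaque counterpart. The claim of a faster rate has no separate support in the global slopes. No baseline-adjusted MGI result is reported at implant level, where the baseline gap is 2.82 - 2.06 = 0.76.

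A reader might infer that the gingivitis effect disappears on adjustment. The documents do not support that: the reported adjusted test is below 0.05, the rebuild gives p = 0.0024 in the same direction, and plaque survives adjustment. Nor can 0.039 be said to fail a multiplicity rule, since none is stated.

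The reported p values follow from the printed statistics. The rebuild assumes 57 patients, an arm split and Gaussian errors, and it inherits the zeros at the last visit in Table 3. If those are missing visits, the sizes would change. Identifying Table 5 as MGI rests on the match in step 5. This should be fixed; it overstates the evidence but does not reverse it.

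**What to change.** 1. Delete the sentence that difference scores and slopes show robustness to the baseline mismatch.
2. In the Conclusions, replace P < 0.001 for MGI with the baseline-adjusted estimate, confidence interval and p value. Use either the reported analysis (p = 0.039) or a re-run that states the number of patients, the model (Gaussian or gamma log-link) and the error df. Label it post hoc if it replaces the planned treatment-by-time test. Give a baseline-adjusted MGI result at implant level as well.
3. Support the claim of a faster rate with the adjusted Day-14 difference or with slopes on actual days, or delete it for the global scores.
4. Correct the Table 5 caption. Check whether the 83%, 57%, 23% and 50% falls are points, and state the base of the 26% and 19%. Check whether the time-3 minimums of 0 in Table 3 are missing visits.

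The cost is rewording and a small re-analysis of existing data. The sponsor gives up P < 0.001 on MGI for a less favourable figure, and any replacement model carries a post hoc label.
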